9.4 Safety Analysis

The overall safety profile of study drug will be assessed in terms of the following safety and tolerability endpoints:

- Adverse events
- Clinical laboratory values (hematology, serum chemistry, urinalysis, and coagulation studies)

Safety endpoints will be analyzed based on the Safety Set. Only descriptive analysis of safety will be performed (i.e., no statistical testing will be performed).

The study period will be divided into 3 segments:

- The **pre-treatment period** is defined as the period after the informed consent/assent date and before the initial dosing of study drug.
- The **treatment-emergent period** is the period at or after the initial dosing (including day 1) of study drug to 28 days after the last dose of study drug.
- The **post-treatment period** is defined as the period after 28 days after last dose until the end of study.

9.4.1 Adverse Events

For analysis purpose, AEs will be categorized as pretreatment AEs, treatment-emergent adverse events (TEAEs), or post-treatment AEs:

- **Pretreatment AE:** any AE that started before initial dosing of study drug.
- **TEAE:** any AE that increased in severity or that was newly developed at or after the initial dosing of study drug to the end of the safety follow up period.
- **Post-treatment AE:** any AE that increased in severity or that was newly developed after 28 days after the last dose of study drug.

For AEs with missing or partial start dates, if there is no clear evidence that the AEs started before or after study treatment, then the AEs will be classified as TEAEs.

As an intermediate step for programming purposes, imputation rules for missing or partially missing AE start/end dates are defined below:

- If year of the AE start date is missing, then query site with no imputation.
- If year of the AE start date is not missing, but both day and month of the AE start date are missing
 - If year of the AE start date = the year of the first dose date, impute the missing day and month of the AE start date using the day and month of the first dose date. If this leads to a date after the AE end date, then impute the missing day and month of the AE start date using the day and month of the AE end date. Note:
 - If the AE ended before first dose date, then the AE will be classified as a pre-treatment AE. If the AE ended after the first dose date, then there is not enough evidence to determine whether the AE is a TEAE or not, and to be conservative, the AE will be classified as a TEAE.
 - If year of the AE start date \neq the year of the first dose date, impute the missing day and month of the AE start date using 1 and Jan. Note:
 - If the year is before the year of the first dose date, then by imputing the missing day and month of the AE start date January 1, TEAE status will be pre-treatment.
 - If the year is after the year of the first dose date, then by imputing the missing day and month of the AE start date January 1, TEAE status will be TEAE if AE

start date is on or before the last dose date +28 days; and will be post-treatment
AE start date is after the last dose date+28 days.

- If month and year of the AE start date are not missing, but day of the AE start date is missing
 - If the year of the AE start date = the year of the first dose date = the year of the AE end date, and the month of the AE start date = the month of the first dose date = the month of the AE end date, then impute the missing day of AE start date using the smaller non-missing value of (day of the first dose, day of the AE end date).
 - If (the year of the AE start date = the year of the first dose date, and the month of the AE start date = the month of the first dose date), and (the year of the AE start date < the year of the AE end date, or the month of the AE start date < the month of the AE end date), then impute the missing day of AE start date using the day of the first dose.
 - Otherwise, impute the missing day of the AE start date as 1.
- Missing or partially missing AE stop date will not be imputed.

An overview of the TEAE profile will be provided with number and percent of subjects including the following categories:

- Number of TEAEs (total number of TEAEs only)
- All TEAEs
- TEAEs by relationship
- TEAEs by maximum severity
- TEAEs leading to treatment discontinuation
- TEAEs leading to treatment interruption
- Serious TEAEs
- Related serious TEAEs
- TEAE leading to death

Adverse events summary tables will be presented for TEAEs only and will include the following:

- All TEAEs
- TEAEs by relationship
- TEAEs by maximum severity
- TEAEs leading to treatment discontinuation
- TEAEs leading to treatment interruption
- Serious TEAEs
- Related serious TEAEs

- TEAEs leading to death

Summaries will be presented by MedDRA system organ class (SOC) and preferred term (PT) using frequency counts and percentages (i.e., number and percentage of subjects with an event). When summarizing the number and percentages of subjects, subjects with multiple occurrences of the same adverse event or a continuing adverse event will be counted once, and only the maximum severity level will be presented in the severity summaries, and the worst/highest relationship level in the relationship summaries.

Additional summary tables will be presented for TEAEs showing number and percentage of subjects

- Any TEAE by PT
- Respiratory TEAE
- TEAE with a frequency of $\geq 5\%$ at the PT level in any treatment group by PT
- TEAE with a frequency of $\geq 5\%$ at the PT level in any treatment group by SOC and PT

In addition, a listing containing individual subject adverse event data for TEAEs leading to treatment discontinuation and treatment interruption, SAEs and all deaths will be provided separately, with a flag indicating the TEAE status for SAEs and deaths.

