12.3.4.1 Adverse Events

AEs will be coded according to MedDRA. The number and percentage of subjects experiencing an AE will be summarized by the MedDRA system organ class and preferred term, as well as by treatment group. AEs will be classified as pretreatment or treatment-emergent.

Pretreatment AEs are defined as AEs that were reported or worsened after signing the ICF up to the start of study drug dosing.

Treatment-emergent AEs are defined as AEs that were reported or worsened on or after the start of study drug dosing through the 28-day Safety Follow-up Visit.

For an AE with a missing or partial start date, if there is no clear evidence that the AE started before or after study treatment, then the AE will be classified as a TEAE.

AE summary tables will be presented for TEAE only by treatment group and will include the following:

- All TEAEs
- TEAEs by relationship
- TEAEs by maximum severity
- TEAEs leading to treatment discontinuation

- Serious TEAEs
- TEAEs leading to death
- Frequently reported TEAEs

Summaries will be presented by MedDRA system organ class and preferred term using frequency counts and percentages (i.e., number and percentage of subjects with an event).

The following rules will apply to the summarization of AEs: (1) a subject with multiple occurrences of the same AE or a continuing AE will only be counted once; (2) only the maximum severity level will be presented in the severity summary; and (3) only the worst relationship level will be presented in the relationship summary.

All AEs through the Safety Follow-up Visit will be listed by subject in a data listing, including pretreatment AEs. AEs leading to death, dose interruption, and permanent discontinuation, as well as SAEs, will be listed separately.

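### SAP 9.4.1 back-dates some adverse events with an unknown start day and no usable end date to before first dose, so they become pretreatment despite the rule that unclear timing means treatment-emergent

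*SAP*

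**What the plan says.** Policy. SAP 9.4.1 sets this rule for events whose onset is not fully dated: "if there is no clear evidence that the AEs started before or after study treatment, then the AEs will be classified as TEAEs". Protocol 12.3.4.1 has the same rule: "if there is no clear evidence that the AE started before or after study treatment, then the AE will be classified as a TEAE".

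Date rules. SAP 9.4.1 then gives imputation rules as a programming aid. Where the start month and year are known and only the day is missing, there are three branches:

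- Branch 1 applies when the years match and "the month of the AE start date = the month of the first dose date = the month of the AE end date". It imputes the smaller non-missing value of the first-dose day and the end day.
- Branch 2 applies when the start month and year are those of first dose and either the end year is later than the start year or "the month of the AE start date < the month of the AE end date". It imputes the first-dose day.
- Branch 3 is the default: "Otherwise, impute the missing day of the AE start date as 1".

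On end dates: "Missing or partially missing AE stop date will not be imputed".

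Periods. In SAP 9.4.1 the TEAE definition runs "to the end of the safety follow up period", while a post-treatment event is one that worsened or was "newly developed after 28 days after the last dose of study drug". SAP 9.4 ends the treatment-emergent period at 28 days after last dose. Protocol 8.1.3 places the Safety Follow-up Visit 4 weeks ± 7 days after last dose.

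**The concern.** Branches 1 and 2 both compare the start with an end month or year. An ongoing event has neither, and an end date with only the year known has no month to compare. Such an event reaches the default even though its start month is the month of first dose, which is exactly where timing relative to dosing is unclear. Day 1 of that month precedes first dose unless dosing began on the 1st, and SAP 9.4.1 defines a pretreatment event as one that started before initial dosing.

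The adverse-event summary tables in SAP 9.4.1 show TEAEs only, and the narrative listings in SAP 9.5 select most adverse events by TEAE status. A misclassified event is lost from those outputs. The affected type, an event with onset around the start of treatment and no recorded resolution, is one a safety reader would want counted.

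The period definitions raise a smaller matter: one event can meet both the TEAE and the post-treatment definition.

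**Working it through.** The documents give no figure to reproduce; this is a check of logic.

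**1. Apply the three branches literally.** Illustrative inputs: first dose 15 September 2016; event start recorded as September 2016, day missing; no worsening recorded.

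| End date recorded | Branch | Imputed start | Class |
|---|---|---|---|
| 20 September 2016 | 1 | 15 September | TEAE |
| 10 September 2016 | 1 | 10 September | Pretreatment (correct) |
| September 2016, day unknown | 1 | 15 September | TEAE |
| 3 November 2016 | 2 | 15 September | TEAE |
| 3 January 2017 | 2 | 15 September | TEAE |
| 2016 only | default | 1 September | Pretreatment |
| None (ongoing) | default | 1 September | Pretreatment |

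The results are the same whether a missing value sorts lowest, as in SAS, or any comparison with a missing value is false.

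**2. Compare with the neighbouring rule.** If both day and month of the start are missing and the year is that of first dose, SAP 9.4.1 imputes the first-dose date, and its note keeps the undetermined event as a TEAE on grounds of caution. So an ongoing event known only to have started in 2016 is a TEAE. The same event known to have started in September 2016 is pretreatment. If it ends on 3 November, it is a TEAE again. Nothing in the SAP explains this pattern.

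**3. When the gap has no effect.** For an ongoing event the imputed day equals the first-dose day only if dosing began on the 1st. Over 2016 and 2017 there are 366 + 365 = 731 possible first-dose dates, of which 24 are the 1st of a month. The other 731 − 24 = 707 (707/731 = 96.7%) give pretreatment. This is a share of calendar dates, not of events.

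**4. Is day 1 a reasonable guess?** Assume, for illustration only, that onset is equally likely on each day of a 30-day month. The chance that it fell on or after first dose on day d is (30 − d + 1)/30. For d = 15 this is 16/30 = 53%; it ranges from 29/30 = 97% (d = 2) to 1/30 = 3% (d = 30). The timing is unclear, which is the case the policy assigns to TEAE.

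**5. Overlap of periods.** The visit window is 28 ± 7, i.e. days 21 to 35 after last dose. Post-treatment starts on day 29. With the visit on day 21 or 28 no day meets both definitions; with the visit on day 35, days 29 to 35 do, which is 35 − 28 = 7 days. The 28-day limit also appears in the SAP 9.4.1 imputation note for events starting in a year after first dose, so the TEAE definition disagrees with that note as well as with SAP 9.4.

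**The case against.** The strongest reply is that the policy is stated first and the imputation is offered only as an intermediate programming step, so the policy governs and a careful programmer would override the day-1 date. This has some force, but the SAP states no order of precedence, and its own notes derive TEAE status from the imputed date. A programmer following the text would produce the misclassification.

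Several limits on size do stand:

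- The event must have its onset in the calendar month of first dose, a known month with an unknown day, and no usable end date. For an ongoing event in a subject who completes the study, that means unresolved at about 28 weeks.
- An event recorded as worsening after first dose is still a TEAE.
- The protocol collects the date of first occurrence for each event (13.1.1.3) and queries missing data (13.3), so partial dates should be few.
- Protocol 12.3.4.1 lists all adverse events including pretreatment ones. The SAP lists serious events and deaths with a TEAE flag, whatever their status. Safety analysis is descriptive, without testing.

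On the overlap, no table of post-treatment events is specified. An event on days 29 to 35 meets the TEAE definition as written and is counted unless a program gives the other label priority.

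**Conclusion.** The rule is wrong as written: for a defined class of events it gives a classification contrary to the stated policy in both documents, in the non-conservative direction. The class is narrow. The documents give no count of partial dates; with about 66 subjects the number affected is probably very small, possibly none.

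Three stronger readings are not supported. A reader might take 97% as the share of events misclassified; it is only the share of calendar dates that are not the 1st of a month. A reader might infer that unresolved events from the first month of dosing are removed generally; ongoing events with complete start dates are unaffected. A reader might infer that safety data are lost; the events leave the TEAE tables but remain in the listings.

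The conclusion rests on the branches being programmed literally and on TEAE status being taken from the imputed date, as the SAP's notes do. The period overlap is real but secondary. It arises only when the follow-up visit falls on days 29 to 35 and is mainly a matter of labelling.

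**What to change.** 1. Extend branch 2. When the start month and year are those of first dose and only the day is missing, impute the first-dose day if the end date is later, missing, ongoing or incomplete, unless the known part of the end date shows that the event ended before first dose. With this change the ongoing case becomes a TEAE on all 731 dates checked. The wording must include incomplete end dates; covering only missing or ongoing ones would leave the year-only case unrepaired.
2. State in SAP 9.4.1 that the unclear-timing rule takes precedence over any imputed date.
3. Choose one upper bound for TEAEs and use it in the SAP 9.4 period definition, both SAP 9.4.1 definitions and the SAP 9.4.1 imputation note, with post-treatment starting after it. Align it with protocol 12.3.4.1, which refers to a 28-day Safety Follow-up Visit although that visit has a ± 7-day window. Either last dose + 28 days or the actual follow-up visit removes the overlap if applied everywhere.

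The cost is a few sentences in SAP 9.4 and 9.4.1, one changed condition and one cut-off in the adverse-event program, and no new data. It should be done before data lock and unblinding.

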9.4.2 Clinical Laboratory

For the laboratory measurements, the raw values and change from baseline values of the continuous hematology and chemistry results will be summarized in SI units by treatment group at each scheduled time point. For hematology and chemistry, the number and percentage of subjects with abnormal low ($<LLN$) value and with abnormal high ($>ULN$) value at each scheduled time point will be summarized.

The number and percentage of subjects with at least one potentially clinically significant (PCS) event for liver enzyme during the treatment-emergent period will be summarized. The PCS criteria are provided in Appendix F.

For all LFT results (alanine aminotransferase [ALT], aspartate aminotransferase [AST], serum alkaline phosphatase [ALP], Gamma-glutamyl transferase [GGT] and total bilirubin), the following analyses will be conducted:

- For each of the LFTs, mean values (and 95% confidence interval) will be plotted against visit, and box plot of LFT value/ULN will be plotted against visit.
- The incidence of PCS LFTs during the treatment-emergent period according to the baseline status will also be summarized by treatment group (only worsening of the shift from baseline will be presented).
- A listing of subjects with elevated LFT results during the treatment-emergent period will be presented. The listing will include all parameters of the LFT assessment at all visits.

Results of urinalysis and the serum pregnancy test will be listed in individual subject data listings only. In addition, a listing containing individual subject hematology, chemistry, and

coagulation values outside the reference ranges will be provided. This listing will include data from scheduled and unscheduled time points.

9.4.3 Vital Signs

For the vital signs measurements, the raw values and change from baseline values will be summarized by treatment group at each scheduled time point: systolic and diastolic blood pressure (mm Hg)

The number and percentage of subjects with at least one PCS vital signs event during the treatment-emergent period will be summarized. The PCS criteria are provided in Appendix F

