12.3.4.4 Vital Signs

The following vital signs will be summarized by treatment group at each scheduled time point: systolic and diastolic blood pressure (mmHg), body temperature, pulse rate (beats per minute), and respiratory rate (breaths per minute). Clinically significant abnormal findings in vital signs will be reported as AEs.

The number and percentage of subjects who meet the abnormal criteria for the vital signs evaluation during the Treatment Period will be tabulated by treatment group: HR \leq 50 bpm and a decrease from baseline \geq 20 bpm, HR \geq 120 bpm and an increase from baseline \geq 20 bpm, systolic blood pressure \leq 95 mm Hg and a decrease from baseline \geq 20 mm Hg, systolic blood pressure \geq 160 mm Hg and an increase from baseline \geq 20 mm Hg, diastolic blood pressure \leq 45 mm Hg and a decrease from baseline \geq 10 mm Hg, diastolic blood pressure \geq 110 mm Hg and an increase from baseline \geq 10 mm Hg, weight \geq 5% increase from baseline, and weight \geq 5% decrease from baseline.

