3 SUMMARY OF MODIFICATIONS

No applicable as of 01 August 2016

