4 INTRODUCTION

This SAP describes the planned final analyses for the Study VX15-809-112 data and is based on the

- approved clinical study protocol (Version 1.0, dated 15 January 2016),
- approved electronic case report form (eCRF) (dated 13 January 2017).

Study VX15-809-112 is a Phase 4, Randomized, Double-Blind, Placebo-Controlled, Parallel-Design Study of the Effect of Lumacaftor/Ivacaftor Combination Therapy on Exercise Tolerance in Subjects Aged 12 Years and Older With Cystic Fibrosis, Homozygous for the *F508del-CFTR* Mutation.

This SAP (Methods) documents the planned final statistical analyses of efficacy and safety introduced in the study protocol of VX15-809-112, and describes the corresponding data presentations. It also documents additional efficacy and safety analyses not specified in the protocol, which will provide supportive information to the scientific understanding of the drug entity.

The [REDACTED] Biostatistics Department will perform the statistical analysis of the efficacy and safety data under the supervision of Vertex Biometrics Department; SAS (Version 9.2, or higher) will be used to generate all statistical outputs (tables, figures, listings, and datasets). The SAP will be finalized and approved prior to the final clinical data lock and treatment unblinding for the study.

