9 STATISTICAL ANALYSIS

9.1 General Considerations

The Schedule of Assessments is provided in Appendix A.

All individual subject data for those randomized or exposed to study drug will be presented in data listings.

Continuous variables will be summarized using the following descriptive summary statistics: the number of subjects (n), mean, standard error (SE), standard deviation (SD), median, minimum value (min), and maximum value (max). The precision of the measurement for each continuous variable will be used to determine the number of decimal places to present in tables, figures, and derived listings. Minimum and maximum values will be reported with the same precision as the units of measure. The mean and median will be reported to 1 greater decimal place, and the SE and SD will be reported to 2 additional decimal places. Any values that require transformation to standard units (metric or SI) will be converted with the appropriate corresponding precision.

Categorical variables will be summarized using counts and percentages. Percentages will be presented to 1 decimal place.

Baseline Value: Unless otherwise specified, the baseline value will be defined as the most recent non-missing measurement (scheduled or unscheduled) collected prior to the initial administration of study drug. Baseline CPET data will be collected on Day 1 prior to the initial administration of study drug. Unscheduled visit measurements will be included for derivation of baseline. For actigraphy variables, baseline data will be defined as the mean of the data collected for the 7 days immediately preceding Day 1 (Day -7 to Day -1) during the Screening Period.

Absolute Change from baseline will be calculated as Post baseline value - Baseline value.

Relative change from baseline will be calculated and expressed in percentages as $100 \times \frac{(\text{Post baseline value} - \text{Baseline value})}{\text{Baseline value}}$.

Unscheduled Visits: Unscheduled visit measurements will be included in listings, for derivation of visit windows and computation of baseline/last on-treatment visit, and for the analysis of maximum/minimum on-treatment values and maximum/minimum changes from baseline values.

Visit Windows: Appendix C defines the visit window mapping rules to derive the analysis visits.

Repeated observations within the same visits window

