12 APPENDICES

Appendix A Schedule of Assessments

Table 12-1 Study VX15-809-112: Treatment Period and Safety Follow-up Visit

Event/Assessment	Treatment Period			Early Termination of Treatment ^a	Safety Follow-up 4 Weeks (± 7 Days) After Last Dose ^a
	Day 1	Week 12 (± 7 Days)	Week 24 (± 7 Days)		
Clinic Visit	X	X	X	X	X
Randomization	X				
CFQ-R, PHQ-8, and GAD-7 ^b	X	X	X	X	
Height and weight ^c	X	X	X	X	X
Vital signs ^d	X	X	X	X	X
Spirometry ^e	X	X	X	X	
Physical examination (PE) ^f	X				X
Ophthalmologic examination			X ^g	X ^g	X ^g
Cardiopulmonary exercise test (CPET) ^h	X	X	X	X	
Urine β-HCG ⁱ	X	X	X	X	X
Serum chemistry ^j	X	X	X	X	X
Hematology ^j	X	X	X	X	X

^a If the subject prematurely discontinues study drug, an Early Termination of Treatment (ETT) Visit should be scheduled as soon as possible after the subject decides to discontinue. If the ETT Visit occurs 3 weeks after the last dose of study drug or later, then the ETT Visit will replace the Safety Follow-up Visit, and a separate Safety Follow-up Visit will not be required. When the Safety Follow-up Visit is complete, the subject has completed the study.

^b All questionnaires must be completed before the start of any other assessments scheduled at that visit. The CFQ-R must be completed first, then the PHQ-8 and GAD-7.

^c During the Treatment Period and at the Safety Follow-up Visit, height will be collected only for subjects who were 21 years of age or younger at the Screening Visit. Height and weight will be measured with shoes off.

^d Vital signs (systolic and diastolic blood pressure, oral temperature, pulse rate, and respiration rate) will be collected before study drug dosing and after the subject has been seated for at least 5 minutes. Blood pressure will be taken using a manual sphygmomanometer.

^e Spirometry will be assessed before CPET.

^f The physical examination includes an assessment of all body systems. Symptom-directed physical examinations will occur at any time during the study if triggered by AEs or if deemed necessary by the investigator.

^g For all subjects <18 years of age at the Screening Visit, except for those who have had bilateral lens removal, an ophthalmologic examination will be conducted by a licensed ophthalmologist or optometrist at 1 of the following visits: the Week 24 Visit, the ETT Visit, or the Safety Follow-up Visit.

^h CPET includes pulse oximetry.

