Appendix F Criteria for Potentially Clinically Significant Events

Table 12-7 Criteria for Potentially Clinically Significant Laboratory Tests

Parameter	PCS	Comments
Clinical Chemistry		
ALT	$\leq 3xULN$ *(Not a PCS criteria) $>3x - \leq 5xULN$ $>5x - \leq 8xULN$ $>3xULN$ $>5xULN$ $>8xULN$	FDA DILI Guidance Jul 2009.
AST	$\leq 3xULN$ *(Not a PCS criteria) $>3x - \leq 5xULN$ $>5x - \leq 8xULN$ $>3xULN$ $>5xULN$ $>8xULN$	FDA DILI Guidance Jul 2009.
ALT or AST	$ALT > 3xULN$ or $AST > 3xULN$	Vertex LFT working group 2014
Alkaline Phosphatase	$>1.5xULN$	FDA DILI Guidance Jul 2009.
Total Bilirubin	$>1.5x - \leq 2xULN$ $>2xULN$	FDA DILI Guidance Jul 2009.
ALT and Total Bilirubin	$ALT > 3xULN$ and $TBILI > 2xULN$	FDA DILI Guidance Jul 2009. To be counted within a same treatment phase, whatever the interval between measurement.
AST and Total Bilirubin	$AST > 3xULN$ and $TBILI > 2xULN$	FDA DILI Guidance Jul 2009. To be counted within a same treatment phase, whatever the interval between measurement.
(ALT or AST) and Total Bilirubin	$(ALT > 3xULN$ or $AST > 3xULN)$ and $TBILI > 2xULN$	Vertex LFT working group 2014

Table 12-8 Criteria for Potentially Clinically Significant Vital Signs

CRITERIA for POTENTIALLY CLINICALLY SIGNIFICANT VITAL SIGNS		
Parameter	PCS	Comments
HR	≤ 50 bpm and decrease from baseline ≥ 20 bpm ≥ 120 bpm and increase from baseline ≥ 20 bpm	To be applied for all positions (including missing) except STANDING.
SBP	>140 mmHg at least once >160 mmHg at least once >140 mmHg at least twice >10 mmHg increase from Baseline at least once >20 mmHg increase from Baseline at least once	To be applied for all positions (including missing) except STANDING.
DBP	>90 mmHg at least once >100 mmHg at least once >90 mmHg at least twice >5 mmHg increase from Baseline at least once >10 mmHg increase from Baseline at least once	To be applied for all positions (including missing) except STANDING.

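### SAP 9.4.3 plans by-visit summaries for blood pressure only, leaving out without explanation the pulse rate, respiratory rate and temperature summaries that protocol 12.3.4.4 commits to

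*SAP*

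**What the plan says.** Protocol 12.3.4.4 lists the measures to be summarised for each arm at every planned visit: "systolic and diastolic blood pressure (mmHg), body temperature, pulse rate (beats per minute), and respiratory rate (breaths per minute"). Protocol 7.2 includes vital signs in its safety and tolerability secondary endpoint, and SAP 6.2 lists them as a safety endpoint.

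SAP 9.4.3 has two parts. First, raw values and changes from baseline "will be summarized by treatment group at each scheduled time point: systolic and diastolic blood pressure (mm Hg"); no other measure is named. Second, "The number and percentage of subjects with at least one PCS vital signs event during the treatment-emergent period will be summarized", with criteria in Appendix F. Table 12-8 there has rows for heart rate, systolic pressure and diastolic pressure only. The heart-rate row counts extremes in either direction, for example at or below "50 bpm and decrease from baseline" of at least 20 bpm.

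The schedule in SAP Appendix A keeps all five measures: "Vital signs (systolic and diastolic blood pressure, oral temperature, pulse rate, and respiration rate) will be collected before study drug dosing". They are due at Day 1, Week 12, Week 24, early termination and safety follow-up.

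SAP 9.1 provides that "All individual subject data for those randomized or exposed to study drug will be presented in data listings".

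**The concern.** The SAP sentence has the same structure as the protocol sentence but stops after blood pressure. Someone programming from the SAP would produce no by-visit table for pulse, respiratory rate or temperature, and the report would lack summaries that the protocol specifies for a listed safety endpoint.

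The SAP does not explain the difference. Its Summary of Modifications reads "No applicable as of 01 August 2016". Its introduction says "It also documents additional efficacy and safety analyses not specified in the protocol", which announces additions and is silent on removals. The protocol leaves analysis details to the SAP, but leaving out named summaries is not a matter of detail.

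What is at stake is descriptive safety reporting. This is a cardiopulmonary exercise trial, and resting pulse and respiratory rate are measures a reader would expect to see side by side by arm. The data will have been collected either way.

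**Working it through.** The documents state no figure to reproduce, so the check is a comparison of texts.

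| Measure | By-arm, by-visit summary in protocol 12.3.4.4 | Collected per SAP Appendix A | By-arm, by-visit summary in SAP 9.4.3 | Row in SAP Table 12-8 |
|---|---|---|---|---|
| Systolic pressure | yes | yes | yes | yes |
| Diastolic pressure | yes | yes | yes | yes |
| Pulse / heart rate | yes | yes | no | yes, extremes only |
| Respiratory rate | yes | yes | no | no |
| Body temperature | yes | yes | no | no |

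Count: 5 committed − 2 planned = 3 missing. Of these three, one keeps a count of extremes and two have no planned tabulation.

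**Does another SAP section fill the gap?** SAP 9.4.4 (pulse oximetry) covers oxygen saturation only. The respiratory adverse event table in 9.4.1 counts events, not rates. Listings under 9.1 show individual values without comparing arms. None of these gives a mean by arm.

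**Can the heart-rate counts stand in for the by-visit mean?** The documents give no pulse data, so this can only be shown over a range of assumptions. Assume 33 subjects per arm, baseline pulse mean 80 and SD 12, and a change with SD 8 to 12 bpm drawn independently of baseline. The standard error of the difference in mean change is SD × √(2/33). The expected count is the number per 33 who reach at least 120 bpm with a rise of at least 20 bpm at one visit (simulated).

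| True rise | SD of change | Standard error | Rise ÷ SE | Expected high-HR subjects per 33, one visit |
|---|---|---|---|---|
| 5 bpm | 8 | 1.97 | 2.5 | 0.08 |
| 5 bpm | 12 | 2.95 | 1.7 | 0.48 |
| 8 bpm | 8 | 1.97 | 4.1 | 0.2 |
| 8 bpm | 12 | 2.95 | 2.7 | 0.8 |

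SAP 9.4.3 counts a subject with at least one event over the whole treatment-emergent period, so one visit understates the count. Over three post-baseline visits, with a rise of 8 bpm, 30 subjects, a common within-subject correlation of 0.5, mean 80 to 85 and SD 12 to 15, the expected number is about 0.2 to 1.8.

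Across these assumptions the count ranges from almost none to about two subjects. It says little about a moderate mean shift, although it need not be zero. A by-visit mean addresses the shift directly, but with limited precision at this sample size. The point does not depend on these figures; it rests on the comparison of texts.

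**The case against.** The strongest reply is that little is lost. Individual values are listed. Under protocol 12.3.4.4 and 13.1.1.2, clinically significant vital-sign findings are reported as adverse events. Heart-rate extremes in both directions are tabulated. The SAP also keeps by-visit resting oxygen saturation, a respiratory adverse event table and by-visit ppFEV₁. Neither document names a pulse, respiratory-rate or temperature signal for this drug. SAP 9.4 restricts safety to descriptive analysis, so no test is forgone, and a descriptive table could be produced later from the same data. All of this stands, and it limits the point to a minor one.

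A reader might infer more than the documents support:

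- **That a shift in these measures would go unseen.** The listings, adverse event reporting and heart-rate counts argue against that. The gap is in planned by-arm mean summaries.
- **That the SAP tabulates nothing but blood pressure.** This is true of the by-visit summaries only, because the same section counts heart-rate events.
- **That the heart-rate count would stay at zero under a real shift.** This holds only for some assumed pulse values at a single visit.
- **That the measures were deliberately dropped.** The list stops where the protocol's list continues, so an unfinished list is possible. The missing full stop settles nothing, since the section's last sentence lacks one too. The modifications section does not say that it tracks departures from the protocol, so its entry is weak evidence either way.

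None of this supplies the three summaries or a reason for leaving them out.

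**Conclusion.** The point holds as a minor inconsistency between protocol and SAP. Three of the five vital-sign summaries specified in protocol 12.3.4.4 are absent from SAP 9.4.3, with no recorded reason, although all five measures are collected. A mean shift by arm in pulse rate, respiratory rate or temperature would appear in no planned summary. The primary analysis, the secondary efficacy analyses and the analysis sets are untouched. The conclusion assumes that the SAP text as given is complete at this place; no redaction is marked there.

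**What to change.** In SAP 9.4.3, add pulse rate, respiratory rate and body temperature to the existing by-arm, by-visit table, with raw values and change from baseline as for blood pressure. The by-visit summary itself restores the protocol commitment. The change-from-baseline columns follow the SAP's own table format, since the protocol sentence does not mention change. If the omission was intended, state the departure from protocol 12.3.4.4 and the reason for it in the SAP.

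The cost is one line of SAP text and three extra parameters in one table, with no new data collection.

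This does not bring the whole section into line with the protocol. Protocol 12.3.4.4 also sets abnormality criteria for low blood pressure and for weight change that have no counterpart in SAP Table 12-8, and these can be reconciled in the same edit.
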